#### Insert: Placebo and Drug-containing (TFV/FTC)

CONRAD 117 was a randomized, double blind, placebo-controlled, Phase 1 trial designed to evaluate safety, PK/PD, and disintegration time after a single use of a vaginal insert containing TFV and/or FTC and during and after 14 days of once-daily use. 49 women were randomized 1:1:1:1 to use inserts containing 40 mg TFV, 40 mg FTC, 40 mg TFV + 40 mg FTC, or placebo. Participants self-administered one insert per day for 14 days. The TFV levels in vaginal aspirate were similar to those after TFV 1% vaginal gel administration associated with protection in a previous clinical study, and levels of TFV-DP in vaginal tissue associated with protection in a nonhuman primate study. Levels of FTC in aspirate and FTC-TP in genital tissue appeared to be at least as high as those seen after oral dosing in women and macaques. Systemic levels of both TFV and FTC were low.

#### TAF/EVG Vaginal Insert

CONRAD will conduct A18-146, a Phase 1 clinical trial of the TAF/EVG vaginal insert. This will be the first-in-human study for the vaginally administered TAF/EVG insert and will evaluate the safety, tolerability, PK, and PD after a single dose. The study will recruit healthy, non-pregnant women aged 18-50 years who are not at risk for pregnancy and at low risk for sexually transmitted infections. Participants will use a single TAF/EVG insert in the clinic and will be randomized to 1 of 2 sample collection groups (2 and 48 hours after dosing or 24 and 72 hours after dosing). Plasma, cervicovaginal fluid and cervical tissue for PK will be collected. It is expected that much lower plasma concentrations will be obtained for all drugs and aid in demonstrating systemic safety and refuting the need for further or extensive systemic PK characterization. CONRAD will keep MTN apprised of any serious AEs that occur in this study.

### **2.7.3 Safety of EVG and TAF**

Oral EVG is currently approved for use as part of combination therapy. For the treatment of HIV infection, oral TAF is also approved for use as part of combination therapies. Therefore, large scale studies examining the safety and tolerability of EVG and TAF are limited to clinical trials where EVG or TAF were administered in combination with other ARVs.

#### Oral EVG

Gilead Study GS-US-183-0101 demonstrated minimal AEs with the use of oral EVG. The study was a randomized, double-blind, placebo controlled, monotherapy phase 1/2 trial with 40 HIV-1 infected participants – a mix of both treatment naïve and treatment experienced (but not currently receiving ARV therapy) individuals. Participants received EVG or placebo for 10 days at 5 dosage levels: 200 mg BID, 400 mg BID, 800 mg QD, 800 mg BID, or 50 mg + 100 mg ritonavir QD. TEAEs of grade 2 or 3 were reported in

27% of participants receiving EVG and 40% of those receiving placebo; no participants reported serious AEs, dosage interruptions, or discontinued from the study.

### Oral TAF

The safety of TAF(Vemlidy®) was assessed based on pooled data through the Week 96 data analysis from 1298 subjects in two randomized, double-blind, active-controlled trials (Gilead Study 108 and Study 110), in adult subjects with chronic hepatitis B and compensated liver disease. The most common adverse reaction (all Grades) reported in at least 10% of subjects in the TAF group was headache. The proportion of subjects who discontinued treatment with TAF or TDF due to adverse reactions of any severity was 1.5% and 0.9%, respectively. Table 5 displays the frequency of the adverse reactions (all Grades) greater than or equal to 5% in the TAF group.

**Table 5: Adverse Reactionsa (All Grades) Reported in ≥5% of Subjects with Chronic HBV Infection and Compensated Liver Disease in Studies Gilead Studies 108 and 110 (Week 96 Analysisb)**

Adverse reaction	Tenofovir alafenamide (TAF) N=866	Tenofovir Disoproxil Fumarate (TDF) N=432
Headache	12%	10%
Abdominal pain c	9%	6%
Cough	8%	8%
Back pain	6%	6%
Fatigue	6%	5%
Nausea	6%	6%
Arthralgia	5%	6%
Diarrhea	5%	5%
Dyspepsia	5%	5%

- a. Frequencies of adverse reactions are based on all treatment-emergent adverse events, regardless of relationship to study product.
- b. Double-blind phase
- c. Grouped term including abdominal pain upper, abdominal pain, abdominal pain lower, and abdominal tenderness.

### EVG and TAF in Combination Therapy

Additional clinical trials of EVG or TAF in HIV-infected individuals were conducted with EVG and TAF as part of combination therapy, administered in combination with other antiretrovirals; thus it is not possible to attribute individual AEs to EVG or TAF. Genvoya is a four drug combination that includes EVG, cobicistat, emtricitabine and TAF.

In clinical trials in antiretroviral treatment-naïve HIV-infected adults, the primary safety assessment of Genvoya was based on Week 144 pooled data from 1733 subjects from two randomized, double-blind, active-controlled trials – Gilead Studies 104 and 111. A total of 866 subjects received one tablet of Genvoya once daily.

The most common adverse event (all grades) reported in at least 10% of subjects in the Genvoya group was nausea. The proportion of subjects who discontinued treatment with Genvoya or Stribild due to AEs (regardless of severity) was 1% and 2%, respectively. The majority of AEs were grade 1. See [Table 6](#) for the frequency of AEs (all grades)  $\geq 5\%$  in the Genvoya group.

**Table 6: Adverse Reactions (All Grades) Reported in  $\geq 5\%$  of HIV-1 Infected Treatment-Naïve Adults Receiving Genvoya or Stribild in Gilead Studies 104 and 111 (Week 144 Analysis)**

Adverse reaction	Genvoya N=866	Stribild N=867
Nausea	11%	13%
Diarrhea	7%	9%
Headache	6%	5%
Fatigue	5%	4%

Insert: Placebo and Drug-containing (TFV/FTC)

In CONRAD 134, an open-label study that assessed in-vivo disintegration time, safety, and product acceptability of 4 placebo vaginal inserts in 32 women aged 18-50 who were not at risk of pregnancy – placebo inserts were found to be safe, with one mild AE reported that was subsequently assessed as being unrelated to study drug. The optimized insert prototypes were found to disintegrate faster and have higher acceptability over first generation inserts.

In CONRAD 117, the first-in-human study of vaginal microbicide inserts using TFV and/or FTC containing vaginal inserts - treatment-emergent adverse events (TEAEs) were minimal; only one TEAE met the pre-specified criterion for the safety endpoint, but this event was in the placebo group. Colposcopy and physical exam findings were minimal, as were changes in microflora and systemic laboratory values.

**2.7.4 Efficacy**

Efficacy data for EVG or TAF containing antiretroviral regimens is summarized in the IB, and in the package inserts for EVG/COBI/FTC/TDF (Stribild, Gilead Sciences, Inc.) and EVG/COBI/FTC/TAF (Genvoya, Gilead Sciences, Inc.).

**2.8 Study Hypotheses and Rationale for Study Design**

**2.8.1 Study Primary Hypotheses**

It is hypothesized that the two dose levels of the TAF/EVG Insert in this study will be safe when applied to the rectum and well-tolerated among healthy individuals who have a history of receptive anal intercourse (RAI).

## 2.8.2 Rationale for Study Design

Rectal microbicides are needed for individuals at risk of acquiring HIV infection through unprotected RAI. It is important to expand the rectal microbicide pipeline with the addition of products from different classes such as EVG, an integrase inhibitor, and TAF, a nucleotide reverse transcriptase inhibitor.

### Rationale for the Dosing and PK Sampling Schedule

MTN-039 is the first study to assess the safety and PK of the TAF/EVG Insert applied rectally. Antiviral activity studies of EVG in tissue explant models have shown that an EVG tissue concentration of at least 1000 ng/g will be efficacious prophylactically against HIV infection. Previous vaginal PK/PD studies suggested that a concentration of 1000 fmol/mg TFV-DP in tissue could be a good predictor of high efficacy against HIV infection. Based on the preclinical and animal data collected to date, the TAF/EVG insert with 20 mg TAF and 16 mg EVG doses will achieve the target tissue concentration of 1000 ng/g EVG and 1000 fmol/mg TFV-DP in humans.

The PK sampling schedule in this study will provide valuable information regarding the rectal TAF/EVG PK profile in humans. This will provide guidance for ongoing product development efforts to develop a combination topical insert containing TAF and EVG.

## 3 OBJECTIVES

### 3.1 Primary Objectives

#### **Safety**

- To evaluate the safety of the TAF/EVG Insert, 20/16 mg administered rectally at two dose levels: 1 insert and 2 inserts

#### **Pharmacokinetics**

- To characterize the systemic and rectal pharmacokinetics of the TAF/EVG Insert, 20/16 mg applied rectally at two dose levels: 1 insert and 2 inserts

### 3.2 Secondary Objective

#### **Acceptability**

- To identify product attributes considered likely to challenge and/or facilitate future sustained use of a TAF/EVG insert applied rectally

### 3.3 Exploratory Objectives

#### **Ex Vivo Efficacy**

- To assess the preliminary (*ex vivo*) efficacy of TAF/EVG after product is inserted rectally

### **Pharmacokinetics**

- To characterize the cervicovaginal pharmacokinetics of the TAF/EVG Insert, 20/16 mg applied rectally at two dose levels: 1 insert and 2 inserts

### **Mucosal Safety**

- To evaluate mucosal safety of the TAF/EVG Insert, 20/16 mg applied rectally at two dose levels: 1 insert and 2 inserts

## **4 STUDY DESIGN**

### **4.1 Identification of Study Design**

MTN-039 is a phase 1, multi-site, open-label, single arm, two-period study of rectal administration of one TAF/EVG Insert, 20/16 mg and then two TAF/EVG Inserts.

### **4.2 Summary of Major Endpoints**

#### **Primary Endpoints:**

##### **Safety**

- All Grade 2 and higher AEs

##### **Pharmacokinetics**

- EVG concentrations in:
  - Blood
  - Rectal fluid
  - Rectal mucosal tissue homogenates
- TAF and TFV concentrations in:
  - Blood
  - Rectal fluid
- TFV-DP concentration in:
  - Rectal mucosal tissue homogenates
  - Rectal mucosal tissue cell isolates

#### **Secondary Endpoint:**

##### **Acceptability**

- Participant report of overall acceptability of the TAF/EVG Insert applied rectally

#### **Exploratory Endpoints:**

##### ***Ex Vivo* Efficacy**

- Changes in HIV-1 replication in colorectal explant culture supernatant
- Anti-HIV activity in rectal fluid
- Anti-HIV activity in cervicovaginal fluid

### **Pharmacokinetics**

- EVG, TAF and TFV concentrations in cervicovaginal fluid

### **Mucosal Safety**

- Rectal histology
- Rectal proteomics
- Rectal metabolomics
- Rectal immunophenotype
- Rectal microbiome
- Cervicovaginal microflora

## **4.3 Description of Study Population**

The study population will consist of HIV-uninfected individuals 18 years of age or older who meet the criteria outlined in Sections [5.2](#) and [5.3](#).

## **4.4 Time to Complete Accrual**

The time to complete accrual is anticipated to be approximately 6-8 months.

## **4.5 Study Groups**

MTN-039 will enroll approximately 20 evaluable participants.

## **4.6 Expected Duration of Participation**

Each participant will be on study for approximately 6-13 weeks. The total duration of the study will be approximately 11 months.

## **4.7 Sites**

Sites selected by the MTN Executive Committee.

# **5 STUDY POPULATION**

## **5.1 Selection of the Study Population**

The inclusion and exclusion criteria in Sections [5.2](#) and [5.3](#) will be used to ensure the appropriate selection of study participants.

### **5.1.1 Recruitment**

Participants will be recruited from a variety of sources, including outpatient clinics, universities and community-based locations. Recruitment materials will be approved by

site Institutional Review Boards (IRBs) prior to use.

### **5.1.2 Retention**

Once a participant is enrolled in MTN-039, study sites will make every effort to retain the participant in follow-up to minimize possible bias associated with loss-to-follow-up. Sites will be responsible for developing and implementing local standard operating procedures (SOPs) to target and ensure high rates of retention.

## **5.2 Inclusion Criteria**

Individuals who meet the following criteria are eligible for study inclusion:

- 1) Individuals who are 18 years of age or older at Screening, verified per site SOP
- 2) Able and willing to provide written informed consent to be screened for and enrolled in MTN-039
- 3) HIV-1/2 uninfected at Screening and Enrollment, per applicable algorithm in [Appendix II](#) and willing to receive HIV test results
- 4) Able and willing to provide adequate locator information, as defined in site SOP
- 5) Able to communicate in spoken and written English
- 6) Available for all visits and able and willing to comply with all study procedural requirements
- 7) In general good health at Screening and Enrollment, as determined by the site IoR or designee
- 8) At Screening, history of consensual RAI at least once in lifetime per participant report
- 9) Willing not to take part in other research studies involving drugs, medical devices, genital or rectal products, or vaccines for the duration of study participation (including the time between Screening and Enrollment)
- 10) Willing to comply with abstinence and other protocol requirements as outlined in [Section 6.7](#)
- 11) For participants of childbearing potential: a negative pregnancy test at Screening and Enrollment
- 12) For participants of childbearing potential: Per participant report at Enrollment, using an effective method of contraception for at least 30 days (inclusive) prior to Enrollment and intending to use an effective method for the duration of study participation. Effective methods include:
  - Hormonal methods
  - Intrauterine device (IUD) inserted at least 30 days prior to Enrollment (but not past the maximum length of recommended usage according to package instructions)
  - Sterilization (of participant or partner, as defined in site SOPs)

- Sexually abstinent as defined by abstaining from penile-vaginal intercourse for 90 days prior to Enrollment and intending to remain abstinent for the duration of study participation; this includes having sex exclusively with individuals assigned female sex at birth

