  - Symptoms, clinical or laboratory diagnosis of active pharyngeal, anorectal, or reproductive tract infection (RTI) requiring treatment per current CDC guidelines (<http://www.cdc.gov/std/treatment>).
  - Current symptomatic urinary tract infection (UTI).

Infections requiring treatment include *Neisseria gonorrhoea* (GC), *Chlamydia trachomatis* (CT) infection, syphilis, active herpes simplex virus (HSV) lesions, or symptomatic genital warts, chancroid, pelvic inflammatory disease (PID), bacterial vaginosis (BV), symptomatic vaginal candidiasis, and trichomoniasis.

*Note: Otherwise eligible participants with an exclusionary UTI, BV and/or candida finding may be re-tested during the screening process.*

- 11) For participants of childbearing potential: Pregnant or breastfeeding at either Screening or Enrollment or planning to become pregnant during study participation

*Note: A documented negative pregnancy test performed by study staff is required for inclusion; however, a self-reported pregnancy is adequate for exclusion from screening/enrollment into the study.*

- 12) For participants of childbearing potential: Last pregnancy outcome 90 days or less prior to Screening

- 13) Has any other condition that, in the opinion of the IoR/designee, would preclude informed consent, make study participation unsafe, complicate the interpretation of study outcome data, or otherwise interfere with achieving the study objectives including any significant uncontrolled active or chronic medical condition.

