### **6.7.2 Prohibited Practices**

[figure not shown]
All participants are to abstain from inserting any non-study products (including rectal medications, enemas, lubricant and sex toys) into the rectum, rectal stimulation with fingers, receptive oral anogenital stimulation and receptive anal intercourse for 72 hours prior to and following clinic visits. Participants should abstain from inserting anything into the vagina for 72 hours prior to each clinic visit, including fingers, spermicides, vaginal medications (including hormones), vaginal douches, lubricants and moisturizers, sex toys (vibrators, dildos, etc.) and vaginal intercourse.

If desired, the IoR may request rapid PSRT consultation to assist in making the determination as to whether or not to proceed with the visit at that time or to reschedule an interim visit. If the decision is made to reschedule an interim visit, any missed procedures (including biopsy collection) should be performed during the interim visit.

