## 7.4 Follow-up Visits

### 7.4.1 Dosing – Visits 3 and 7

The first dosing visit (Visit 3) should occur at least 7 days after the Enrollment Visit. The second and final dosing visit (Visit 7) should occur at least 7 days after the last tissue sampling visit following Dose 1 (following Visit 5 or 6 with a 1- to 7-week washout period).

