**Table 12: Dosing Procedures**

Dosing Procedures – Visits 3 and 7	
Component	Procedures

Administrative and Regulatory		
 
Review/update locator information
 
Provide reimbursement
 
Schedule next visit/contact
 

Behavioral/Counseling		
 
HIV pre- and post-test counseling*
 
HIV/STI risk reduction counseling*
 
Protocol counseling
 

Clinical		
 
Review/update medical history
 
Review/update concomitant medications
 
Perform targeted physical examination*
 
Perform genital examination*
 
Perform pelvic examination* ▲
 
Perform rectal examination
 
Treat or prescribe treatment for RTI/UTI, or STIs*
 
Provide available test results
 
Collect/update AEs
 

Laboratory	Pharyngeal	
 
NAAT for GC/CT*
 

	Urine	
 
NAAT for GC/CT* ▼
 
Urine dipstick/culture*
 
Pregnancy test* ■
 

	Blood	
 
CBC with differential and platelets*
 
Chemistries (AST/ALT/creatinine)*
 
Syphilis serology*
 
HIV-1/2 test*
 
Blood for PK ◆
 

	Pelvic▲	
 
CVF for PK **
 
CVF for PD ♣
 
CVF for microflora ♣
 
NAAT for GC/CT/TV*
 

	Anorectal	
 
Rectal fluid for PK **
 
Rectal fluid for PD ♣
 
Rectal fluid microbiome ♣
 
Rectal tissue for PK ♣
 
Rectal tissue for PD ♣
 
Rectal tissue for biomarkers ♣
 
NAAT for GC/CT*
 

Study Product/Supplies		
 
Administration of study product
 
Offer condoms
 
Offer lubricant
 

\* If indicated ▲ Participants assigned female sex at birth and if anatomy allows ▼ If pelvic GC/CT cannot be performed ■ Participants of childbearing potential

◆ All participants will have blood collected at 1, 2, 4, and 6 hours following product administration.

♣ Group 1 only at 2 hours post-dose

\*\* Group 1: 2 and 6 hours post-dose; Group 2: 4 hours post-dose

## 7.4.2 Post-Dosing Visits – Visits 4 and 8

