**Table 14: Other Post-Dosing Visits**

Other Post-Dosing Visits - Visits 5, 6, 9, and 10		
Component	Procedures	
Administrative and Regulatory	
 
Review/update locator information
 
Provide reimbursement
 
Schedule next visit/contact
 
	
Behavioral/Counseling	
 
HIV pre- and post-test counseling*
 
HIV/STI risk reduction counseling*
 
Protocol counseling
 
Behavioral In-Depth Interview (IDI) (Visit 10 only)
 
	
Clinical	
 
Review/update medical history
 
Review/update concomitant medications
 
Perform targeted physical examination*
 
Perform genital examination*
 
Perform pelvic examination* ▲
 
Perform rectal examination
 
Treat or prescribe treatment for RTI/UTI, or STIs*
 
Provide available test results
 
Collect/update AEs
 
	
Laboratory	Pharyngeal	
 
NAAT for GC/CT*
 

	Urine	
 
NAAT for GC/CT* ▼
 
Urine dipstick/culture*
 
Pregnancy test* ■
 

	Blood	
 
CBC with differential and platelets* (required at Visit 10)
 
Chemistries (AST/ALT/creatinine)* (required at Visit 10)
 
Syphilis serology*
 
HIV-1/2 test* (required at Visit 10)
 
Blood for PK
 

	Pelvic ▲	
 
CVF for PK △
 
CVF for PD △
 
NAAT for GC/CT/TV*
 

	Anorectal	
 
• Rectal fluid for PK △
 
• Rectal fluid for PD △
 
• Rectal enema prior to biopsy collection △
 
• Rectal tissue for PK △
 
• Rectal tissue for PD △
 
• NAAT for GC/CT*
 

Study Product/Supplies		
 
• Offer condoms
 
• Provide home enema kit (Visit 6 only)
 

\* If indicated ▲ Participants assigned female sex at birth and if anatomy allows ▼ If pelvic GC/CT cannot be performed ■ Participants of childbearing potential

△ Group 1 will have biopsies, rectal fluid and cervicovaginal fluid (if applicable) collected at 48 hours (Visits 5 and 9) following each administration of product;

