## 9.3 General Criteria for Permanent Discontinuation of Study Product

A participant will be permanently discontinued from product use by the IoR/designee for any of the following reasons:

- Acquisition of HIV infection; for those who acquire HIV, study product should be held beginning immediately upon recognition of the first positive/reactive HIV test
- Pregnancy or breastfeeding
- Anogenital STIs
- Participant is unable or unwilling to comply with required study procedures, or otherwise might be put at undue risk to their safety and well-being by continuing product use, according to the judgment of the IoR/designee.
- Reported use of or need for PrEP or PEP. Participants who experience a known or potential HIV exposure during study participation or have a recognized risk of exposure and thus need PEP or PrEP will have study product permanently discontinued and will be referred for PEP or PrEP initiation. Those who need PEP will be encouraged to start it as quickly as possible and within 72 hours of potential exposure. Since continued study follow-up would be of no benefit following permanent discontinuation of study product use, these participants will be exited from the study.
- Anticoagulant use (e.g., heparin, Lovenox, warfarin and Plavix)
- Use of certain CYP3A inhibitors and inducers (as specified in [Table 8](#) and [Table 9](#))
- Participant develops a Grade 4 adverse event.

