## 8.3 Laboratory Evaluations

The number and percentage of participants with a positive result for the following laboratory tests will be displayed in a table overall and by site: hCG for pregnancy and HIV. A listing of participants with positive results of STI testing (syphilis, trichomonas, gonorrhea, chlamydia) after dose administration will be presented.

Hematology results after dosing with each regimen, including hemogram (hemoglobin, hematocrit, MCV, platelets, WBC) and differential (neutrophils, lymphocytes, monocytes, eosinophils, and basophils) results will be tabulated by dosing regimen using descriptive statistics.

Serum chemistries (AST, ALT, and creatinine) after dosing with each dosing regimen will be tabulated by dosing regimen using descriptive statistics.

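### Pregnancy ends product use and participation, but no pregnancy test is required after Enrollment, so dose 2 falls at least 16 days after the last required test

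*Protocol*

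**What the plan says.** **Entry.** Inclusion criterion 11 (Protocol 5.2) reads "For participants of childbearing potential: a negative pregnancy test at Screening and Enrollment". Exclusion criterion 11 (5.3) covers anyone "Pregnant or breastfeeding at either Screening or Enrollment or planning to become pregnant during study participation". The note under it requires a documented negative test done by study staff before inclusion, whereas a self-reported pregnancy is enough to exclude.

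**After entry.** Section 9.3 lists "Pregnancy or breastfeeding" among the reasons for permanent discontinuation of product. Sections 7.5.2 and 9.5 add termination from the study, follow-up to the pregnancy outcome and, for live births, infant information at about one year.

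**Testing schedule.** Table 12 lists "Pregnancy test" at Visits 3 and 7 with the asterisk that means if indicated. Tables 13, 14 and 15 use the same mark. Appendix I shows a required test only at Screening and Enrollment. At Visit 10, by contrast, Table 14 marks the CBC, the chemistries and HIV as required; the HIV entry reads "HIV-1/2 test* (required at Visit 10)".

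**Timing.** Section 7.4.1 places Visit 3 at least 7 days after Enrollment, and Visit 7 after the last dose 1 tissue visit, "following Visit 5 or 6 with a 1- to 7-week washout period".

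**Reporting.** SAP 8.3 tabulates the number and percentage of participants with a positive result for "hCG for pregnancy and HIV", overall and by site. It states no denominator.

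**The concern.** The protocol does not accept self-report as evidence of non-pregnancy at entry, a visit at which no product is given. Before each actual exposure it requires nothing firmer than an updated history, self-reported symptoms and reported contraception. No passage defines when the test is indicated.

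The safety rule in 9.3 acts only on a pregnancy that someone has recognised. An early pregnancy without symptoms could therefore be exposed to one insert, two inserts or both. Protocol 2.8.2 describes this as the first study of the insert given rectally. If the pregnancy stayed unrecognised to the end of the study, the follow-up in 7.5.2 and 9.5 would not start. Visit 11 may be a phone contact, so Visit 10 can be the last in-person opportunity, and the test is not required there either.

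The SAP table carries the same weakness. Without a stated number tested after dosing, a reader cannot tell how much testing stands behind a low percentage.

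**Working it through.** **1. Required tests after Enrollment.** Visits 3 and 7 (Table 12), 4 and 8 (Table 13), 5, 6, 9 and 10 (Table 14) and 11 (Table 15) make nine contacts. The pregnancy test is if indicated at all nine, so required tests number 0 of 9. Appendix I agrees.

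**2. Days from the last required test to each dose.** Inputs:
- Enrollment is Day 0. Visit 3 is on Day 7 or later (7.4.1).
- The last dose 1 tissue visit is 2 days after Visit 3 in Group 1 (48 hours, Visit 5) or 3 days after in Group 2 (72 hours, Visit 6) (7.3).
- Washout is 7 to 49 days (7.4.1).

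Formula: Visit 7 day = Visit 3 day + 2 or 3 + washout.

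With Visit 3 on Day 7:
- Group 1: 7 + 2 + 7 = Day 16, to 7 + 2 + 49 = Day 58.
- Group 2: 7 + 3 + 7 = Day 17, to 7 + 3 + 49 = Day 59.

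Dose 1 is therefore at least 7 days after the last required test, and dose 2 is 16 to 59 days after it. Counted from dose 1, dose 2 is 2 + 7 = 9 to 3 + 49 = 52 days later. Section 7.4.1 gives no upper limit for Visit 3. If Visit 3 fell on Day 14, which is an assumption, the latest dose 2 would be 14 + 2 + 49 = Day 65 or 14 + 3 + 49 = Day 66.

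**3. Check against the plan's own duration.** Section 10.7.4 gives about 21 to 77 days for the two dose evaluations, without stating the start point. I count from Enrollment. Visit 10 is Visit 7 + 3 days, and Visit 11 is Visit 10 + 3 to 7 days (7.4.4).
- Earliest Visit 11: 16 + 3 + 3 = Day 22 (Group 1), or 17 + 3 + 3 = Day 23 (Group 2). This is close to the stated 21.
- Latest Visit 11 with Visit 3 on Day 7: 58 + 3 + 7 = Day 68, or 59 + 3 + 7 = Day 69. This falls short of 77.
- Day 77 is reached in Group 2 if Visit 3 is on Day 15: 15 + 3 + 49 + 3 + 7 = 77. Dose 2 is then on Day 15 + 3 + 49 = 67.

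The lower end reproduces approximately. The upper end fits only if Visit 3 is later than Day 7, so 59 days is not a ceiling.

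**4. How many participants.** Section 7.3 plans at least three participants assigned female sex at birth in each of two groups, so at least 3 × 2 = 6 of about 20. The number of childbearing potential is not given. Without a pregnancy rate, expected events cannot be calculated.

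**5. What the SAP percentage rests on.** SAP 8.3 limits the STI listing to results after dosing but puts no such limit on the hCG and HIV table. The required Screening and Enrollment tests could therefore feed it. SAP 6.1.5 tabulates completion of required and expected procedures by participant-visit, which may or may not count if-indicated tests. Neither section states how many participants were tested after each dose.

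**The case against.** The strongest reply is that the schedule is internally consistent. The criteria, the visit tables and Appendix I all say required at Screening and Enrollment and if indicated later, and a rule that acts once pregnancy is recognised is compatible with that. There are also real safeguards. Criterion 12 requires at least 30 days of an effective method, or 90 days of abstinence, with intent to continue. Those planning pregnancy are excluded. Contraception counseling begins at Screening. History is updated at each dosing visit, participants are encouraged to report signs of pregnancy, and the test is available.

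This stands to the following extent. A reader might infer that the 9.3 rule cannot work, or that a pregnant participant's eligibility has lapsed. The documents support neither. The rule can work through history, self-report and indicated testing, and eligibility is formally assessed only at Screening and Enrollment. What a pregnant participant would meet at dosing is the discontinuation criterion. The reply does not explain why staff-documented proof is demanded when no product is given but not at exposure, nor why Visit 10 requires three other safety tests and not this one.

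A reader might also infer that a reported 0% positive hCG would mean nobody was tested. That does not follow, because SAP 8.3 does not confine the table to post-dose tests. The defect is an unstated denominator.

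Finally, one might argue that contraception fails as a safeguard because criterion 12 accepts hormonal methods without exception while 6.7.2 bars inserting items into the vagina for 72 hours before each visit, "including fingers, spermicides, vaginal medications (including hormones), vaginal douches". That is too strong. No passage mentions a ring or addresses a method already in place, other methods are accepted, and the washout leaves room for scheduling. It is a wording point.

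**Conclusion.** The concern holds as a gap between the pregnancy rule and the test schedule. Followed exactly as written, the plan allows both doses without a pregnancy test after Enrollment: at least 7 days for dose 1, and at least 16 days for dose 2. The dose 2 interval is 59 days with Visit 3 on Day 7 and a seven-week washout in Group 2, and longer if Visit 3 is later. The consequence is a possible, not a certain, unrecognised exposure and lost follow-up. Its probability cannot be computed from the documents, and contraception lowers it. The primary endpoints are not affected. The change is worth making because it is cheap and concerns participant safety.

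The conclusion rests on the supplied text. The study-specific procedures manual, Letters of Amendment 01 to 03 and the visit-schedule figures were not available, so a Visit 3 window, a definition of indicated or an added test there cannot be excluded. Letter of Amendment 04 states that it leaves the visit schedule unchanged and lists no change to pregnancy testing.

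**What to change.** **Protocol.** The protocol team should reconcile the discontinuation rule in 9.3 and the entry requirement in 5.2 and 5.3 with the if-indicated marking in Table 12, Table 14 and Appendix I. The urine test already listed at those visits can be used, so that the pregnancy rule can operate at the time of each dose. How testing bears on dosing is for the team to decide. If the outcome were a test at Visits 3, 7 and 10, the cost would be three urine tests and a few minutes per participant of childbearing potential: 3 × 6 = 18 tests if six participants qualified (an assumption), plus one schedule edit.

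**SAP 8.3.** Report post-dose hCG positives over participants actually tested in each dosing period, separately from the Screening and Enrollment tests. This costs one sentence and one column. SAP version 2.0 is dated October 2021 and describes a monitoring review held in December 2020, so this may be the part most readily changed.

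**Minor wording.** Clarify how hormonal methods in criterion 12 fit with the 72-hour restriction on vaginal hormones in 6.7.2.
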